7.5.1.2.4 Action taken with study treatment

Any action on study treatment to resolve the AE is to be documented using the categories listed below.

- Drug withdrawn
- Drug interrupted
- Dose reduced
- Dose not changed
- Dose increased
- Not applicable
- Unknown

7.5.1.2.5 Other specific treatment(s) of adverse events

- None
- Remedial drug therapy
- Other

7.5.1.2.6 Outcome

The outcome of the AE is to be documented as follows:

- Recovered/resolved
- Recovering/resolving
- Recovered/resolved with sequelae
- Not recovered/not resolved
- Fatal
- Unknown

7.5.1.3 Assessments and documentation of adverse events

Subjects must be carefully monitored for AEs. All AEs occurring after signed informed consent was obtained must be fully recorded in the subject's CRF.

Documentation must be supported by an entry in the subject's file. A laboratory test abnormality occurring after screening considered clinically relevant, eg, causing the subject to

withdraw from the study, requiring treatment or causing apparent clinical manifestations, or judged relevant by the investigator, should be reported as an AE. Each event should be described in detail along with start and stop dates, severity, relationship to investigational product, action taken, and outcome.

7.5.1.4 Reporting of serious adverse events

The definition of serious adverse events (SAEs) is given in Section 7.5.1.1.

Investigator's notification of the sponsor

All investigators will be thoroughly instructed and trained on all relevant aspects of the investigator's reporting obligations for SAEs. This information, including all relevant contact details, is summarized in the investigator site file. This information will be updated as needed.

All SAEs occurring during the observation period defined in Section 7.5.1.3 must immediately (within 24 hours of the investigator's awareness) be reported to the recipient detailed in the manual. An SAE form must also be completed within 24 hours of the investigator awareness and forwarded to the designated recipient. Each SAE must be followed up until resolution or stabilization by submission of updated reports to the designated recipient.

SAEs occurring after the protocol-defined observation period will be processed by the sponsor according to all applicable regulations.

Notification of the Independent Ethic Committees (IECs) / Institutional Review Boards (IRBs)

Notification of the IECs / IRBs about all relevant events (eg, SAEs, suspected, unexpected, serious adverse reactions [SUSARs]) will be performed by the sponsor and/or by the investigator according to all applicable regulations.

Notification of the authorities

The processing and reporting of all relevant events (eg, SAEs, SUSARs) to the authorities will be done by the sponsor according to all applicable regulations.

Sponsor's notification of the investigational site

The sponsor will inform all investigational sites about reported relevant events (eg, SUSARs) according to all applicable regulations.

7.5.1.5 Expected adverse events

For this study, the applicable reference document is the most current version of the investigator's brochure (IB).

Overview listings of frequent events that have occurred so far in the clinical development are shown in the current IB. If relevant new safety information is identified, the information will be integrated into an update of the IB and distributed to all participating sites.

The expectedness of AEs will be determined by the sponsor according to the applicable reference document and according to all local regulations.

7.5.2 Pregnancies

Not applicable in this pediatric male subject population.

7.5.3 Further safety

7.5.3.1 Vital signs

Systolic and diastolic blood pressure, heart rate, and body temperature will be measured at **all visits**. **Blood pressure may be deferred in infants if appropriate size cuff or equipment is not available. (as of Amd 1)**

7.5.3.2 Physical examination

A complete physical examination including the measurement of body height, weight and temperature will be performed at the Screening visit and at the Month 6 (or final visit). **Body length will be measured instead of height, as age appropriate. (as of Amd 1)**

At the **other** visits, **and during the (as of Amd 1)** optional extension study (every 6 months until switch to commercial drug), only the subject's body height, temperature and weight will be measured.

7.5.3.3 Standard safety laboratory

The following blood (as of Amd 1) samples will be collected at Screening and Month 6 (or final visit):

- CBC with differential: erythrocytes, hemoglobin, hematocrit, platelets, leukocytes, neutrophils, eosinophils, basophils, monocytes, and lymphocytes
- **Serum chemistry (electrolytes (sodium [Na], potassium [K], bicarbonate [CO], chloride [Cl], creatinine, alanine and aspartate aminotransferases [ALT, AST], total bilirubin) (as of Amd 1)**

The following blood samples will be collected at Baseline and Month 6 (or final visit) (as of Amd 1):

- HSP-70 antibody **(except in subjects <7kg) (as of Amd 1)**

7.5.3.4 Inhibitor testing

Premise for inclusion **requires confirmed diagnosis of severe hemophilia A (<1% FVIII) and documentation of a (as of Amd 1)** negative test result of inhibitor at Baseline.

Blood samples for FVIII inhibitor testing will be taken at Screening (**PTPs and MTPs only**), Baseline, **at regularly scheduled intervals throughout the study, and at the (as of Amds 1 and 6)** final visit. The premise for inclusion of **PTPs and MTPs** in this study is the availability of a negative inhibitor **result (as of Amds 1 and 6)** as measured in the blood sample at Screening **and Baseline (as of Amd 7)**. A further sample will be taken at baseline before the first **infusion (as of Amd 1)**. If the inhibitor testing result changes from negative at screening

to positive at baseline, before the first *infusion (as of Amd 1)* of study medication, the subject must be withdrawn from the trial.

In Part B, the requirement for a FVIII inhibitor testing before study entry (as of Amd 1) is not applicable for PUPs but is applicable for MTPs (as of Amd 6). The absence of inhibitors will be assessed using central laboratory testing at Screening (<0.2 BU/mL), with confirmation using local laboratory testing at Baseline (<0.6 BU/mL) (as of Amd 7). After treatment is started (as of Amd 1), PUPs/MTPs must be tested for inhibitor development every 3-5 ED until 20 ED are accumulated (as of Amd 6), and at the final visit (50 ED) (as of Amd 7). Afterwards, blood samples for inhibitor testing and determination of FVIII:C trough level (>48 h after last FVIII treatment) are to be taken:

- ***every 6 months in the extension study until finalization of the study, and at the final visit (as of Amds 1 and 6).***

The laboratory analyses will be performed at central laboratories.

Investigators will be provided with a detailed laboratory manual and a copy of the individual results. Inhibitor testing will be done according to the Nijmegen modified Bethesda inhibitor assay ***at the central laboratory (as of Amd 1)***. A positive inhibitor testing is defined with a threshold of ≥ 0.6 BU in the central laboratory. Any positive test must be confirmed by a second ***plasma (as of Amd 1)*** sample ***and a determination of recovery should be performed. (as of Amd 6)***

For any subject confirmed positive for inhibitors, epitope mapping will be performed (see Section 7.6.1 for details). (as of Amd 4)

Remaining rest of the plasma samples collected at specified study visits could be used for immunology or additional coagulation analysis, or for clarification of any clinical or laboratory adverse event and in no case for genetic analyses. (as of Amd 6)

7.6 Other procedures and variables

7.6.1 Epitope mapping (as of Amd 4)

In the event a subject tested positive for inhibitor, additional blood, up to a maximum allowable as described in Table 14-4a, should be taken to confirm the result (retesting). If the result upon retesting is also positive, epitope mapping will be performed with the additional blood sample that was taken. Details of sample collection and shipment procedures will be provided in the Laboratory Manual. (as of Amd 4)

7.6.2 Biomarker investigation (pharmacogenetics) (recommended – consent required) (as of Amd 4 and Amd 7)

The purpose of this genetic analysis is to identify markers for risk of inhibitor development in subjects treated with BAY 81-8973. The markers to be analyzed are type of FVIII gene mutation if not available, single nucleotide polymorphisms (SNPs) in immunoregulators (eg, IL 10), HLA genotype, and FVIII polymorphisms. This biomarker analysis is exploratory and will be analyzed for PUPs and MTPs only. (as of Amds 4 and 6)

A separate informed consent for pharmacogenetic sampling is required and participation is recommended. (as of Amd 4 and Amd 7)

If a subject elects to participate, a blood sample can be collected at any visit except Screening, ideally at Visit 3 or whenever the subject's body weight/condition is suitable for an additional blood draw. Samples will be prepared and labeled according to laboratory specifications. Details of the sample collection and shipment procedures will be provided in the Laboratory Manual. (as of Amd 4)

A subject does not need to agree to participate in the pharmacogenetic sub-study to be enrolled in the main study. (as of Amd 4). However, as this analysis provides important information about inhibitor development, participation in the sub study is recommended. (as of Amd 7)

7.7 Appropriateness of procedures / measurements

All procedures / measurements are established and validated in this therapeutic area. The assessments closely follow the recommendations specified in CPMP/BPWG/1561/99.

8. Statistical methods and determination of sample size

8.1 General considerations

Statistical analyses will be performed using SAS release 9.1 or higher (SAS Institute Inc., Cary, North Carolina [NC], United States of America [USA]). The version used will be specified in the Statistical Analysis Plan. (As of Amd 1)

8.2 Analysis sets

Efficacy and safety data will be collected from all subjects who received study medication. The intent-to-treat (ITT) population will include all subjects randomized into the study who received study drug. The per-protocol population will exclude subjects who are deemed invalid in the Validity Review Report. Subjects from Part A and Part B will be summarized separately. (as of Amd 1)

8.3 Variables

Baseline

Demographic characteristics, including age, weight, height and race as well as previous exposure to FVIII will be presented for all treated subjects, in the form of summary statistics. Other baseline characteristics, including laboratory findings and vital signs, will be handled similarly.

Extent of Exposure

Extent of exposure to the study drug, including *treatment (as of Amd 1)* characteristics, will be documented in subject diaries and summarized for each subject receiving any amount of drug.

Safety

Safety data will be summarized for all subjects in the safety population. Laboratory findings, AEs, concomitant medications, and medical history data will be provided in subject listings.

Laboratory values and vital signs will be summarized. Individual listings of AEs [including AEs as reported, start, duration, severity, relation to study drug] will be provided. The incidence of treatment-emergent AEs will be summarized using the Medical Dictionary for Regulatory Affairs (MedDRA). *(some text deleted as of Amd 1)*

Inhibitor development, as measured by Nijmegen assay, will be summarized by time point and presented in subject listings. *The purpose of the listing is to delineate the clinical factors which may be positively associated with development of the inhibitor. (as of Amd 1)*

The frequency of subjects who develop positive inhibitor titers (Bethesda ≥ 0.6 BU) and *confirmed by repeat measurement (as of Amd 1)* will be presented by time point. *If the inhibitor value drops below 0.6 BU on repeat measure without intervention, the inhibitor will be determined as being transient. We will classify inhibitor patients as being either low titer or high titer based upon persistence of an inhibitor >5 BU. (as of Amd 1)* The rate of inhibitor development associated with BAY 81-8973 will be determined. Subjects with no inhibitors are required to have at least 50 ED to be counted in the denominator.

Efficacy

Efficacy data will be summarized for all subjects in the *intent-to-treat (as of Amd 1)* (ITT) population. The primary efficacy variable will be the annualized number of *total bleeds (sum of spontaneous bleeds and traumatic bleeds) (as of Amd 1)* within 48 h after a prophylaxis infusion *(as of Amd 1)*. Other variables summarized will be the physician's/subject's/parents' *(as of Amd 1)* assessment of the response to treatment of bleeds (excellent, *good, moderate, poor*) *(as of Amd 1)* and during surgeries. The number of treatments required to control bleeds, the *proportion (as of Amd 1)* of prophylaxis infusions with less than expected therapeutic effect (LETE) (defined as a prophylaxis infusion followed by a bleed within 48 h), annualized number of *total bleeds (sum of spontaneous bleeds and trauma bleeds) (as of Amd 1)* during prophylaxis, FVIII usage and recovery will be summarized. *A detailed Statistical Analysis Plan will be provided (as of Amd 1).*

Pharmacokinetics / pharmacodynamics (Optional)

For investigation of drug exposure and potential relationships to drug effects, selected subjects will participate in pharmacokinetic (PK) sampling. Any subject's participation in PK sampling is voluntary and consent/*assent is required (as of Amd 1)*.

Based on the known PK of FVIII in hemophilia subjects it is expected that a *reduced (as of Amd 1)* sampling strategy will be sufficient to calculate relevant pharmacokinetic parameters.

Blood samples for population PK analyses will be collected according to a sampling schedule. Blood sampling for the determination of FVIII:C in plasma will be taken at baseline *before the infusion (pre-infusion)* at 20-30 minutes, *4 h, and 24 h* after end of *infusion*. *Attempt should be made to collect the sample as close as possible to the times indicated above. If there is a delay in collecting a sample, the sample should still be collected so that there are at least 3 samples post infusion. In all cases the exact time of start and end of infusion and the time of actual sample collection should be noted in the CRF. (as of Amd 1)*

A minimal number of 6 subjects is required. The following parameters will be calculated: C_{max} , AUC, recovery, clearance, MRT and $t_{1/2}$ using non-compartmental methods.

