7.2 Population characteristics

7.2.1 Demographic

Demographic characteristics to be recorded at Screening will include age and race. In addition, a complete physical examination including pulse, blood pressure, body temperature, height, weight, and a review of body systems will be performed and the results documented.

If known, any gene mutation should be noted (as of Amd 3).

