8.4 Statistical and analytical plans

The data will be summarized using the software package SAS release 9.1 or higher (SAS Institute Inc., Cary, North Carolina [NC], United States of America [USA]). All data will be listed and summary tables will be provided. The number of data available and missing data, mean, standard deviation, and other summary statistics will be calculated for continuous data. Frequency tables will be generated for categorical data. No formal statistical tests will be performed.

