6.4 Safety

All subjects receiving any amount of study drug will be included in the safety analysis. Laboratory findings, adverse events, concomitant medications, and medical history data will be provided in subject listings.

Laboratory values, incidence of high or low abnormal values, changes from baseline (Baseline value is the last value before the first study drug infusion.) will be summarized. Vital signs will be summarized. Individual listings of AEs [including AEs as reported, start, duration, severity, relation to study drug] will be provided. The incidence of treatment-emergent AEs will be summarized using the Medical Dictionary for Regulatory Affairs (MedDRA). AEs with a start date prior to first infusion or more than 3 days after the last infusion are not treatment emergent. Treatment emergent determination will be derived after missing or incomplete AE start date is imputed. Imputation rules for missing and incomplete AE start are described in Section 4.3

Two laboratory analytes, Anti HSP70 and Anti BHK, will be summarized in a listing that will include all values for those subjects with any positive result. Incidence of HSP-70 antibody formation and hamster protein antibody formation will be assessed from these laboratory tests.

Inhibitor development, as measured by Bethesda assay, as well as the results from all ELISA assays, will be summarized by preparation and timepoint and presented in subject listings. The frequency of subjects who develop positive inhibitor titers (Bethesda ≥ 0.6 BU) will be presented.

Vital signs and change from baseline of vital signs will be summarized with descriptive statistics distinguishing pre-infusion and post-infusion readings. Baseline is the last measurement before the first study drug infusion. Post-infusion minus pre-infusion values will be summarized at Month 1, Month 2, and final visit in the main study.

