6.1.3 Disease history

The following baseline characteristics of the disease history will be evaluated descriptively for the ITT, by pre-treatment (PUPs/MTPs) and overall:

- Age of hemophilia diagnosis
- Start of therapy (MTPs)
- Family history of hemophilia
- FVIII level and type of assay
- Family and personal history of past inhibitor formation
- Number and type of bleeds in the past 12 months
- Presence and location of target joints

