6.4.3 Laboratory parameter

Laboratory values, incidence of high or low abnormal values, and changes from baseline will be summarized. In general only central laboratory values will be used for analysis. Where also local values are taken into consideration will be explicitly mentioned.

Two laboratory analytes, Anti HSP-70 and inhibitors, will be summarized in a listing that will include all values for those subjects with any positive result. Incidence of HSP-70 antibody formation and inhibitors will be assessed.

Inhibitor development, as measured by Bethesda assay will be summarized timepoint and presented in subject listings. The frequency of subjects who develop positive inhibitor titers (Bethesda ≥ 0.6 BU) as well as high titer (> 5.0 BU) will be presented. For the inhibitors as well as for the high titer inhibitors Kaplan Meier graphics for the occurrence will be provided.

A positive inhibitor testing is defined with a threshold of ≥ 0.6 BU in the central laboratory and a confirmation by

- a second plasma sample and a positive central testing or
- two consecutive local measurements (2^{nd} and 3^{rd} sample) with doubled threshold (Bethesda ≥ 1.2 BU).

In case a central value of the same samples used for local confirmation shows no inhibitor, the local confirmation is not valid.

High titer inhibitor needs not to be confirmed by a second high (> 5.0 BU) value, but the inhibitor itself needs a confirmation.

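### Protocol 8.3 relies on a listing to find factors associated with inhibitor development, and the Part B SAP text does not plan to tabulate disease history or FVIII mutation by inhibitor status

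*Protocol*

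**What the plan says.** **Protocol.** Section 8.3 (Safety) states: "Inhibitor development, as measured by Nijmegen assay, will be summarized by time point and presented in subject listings". It then gives the reason for the listing: "The purpose of the listing is to delineate the clinical factors which may be positively associated with development of the inhibitor". It names no candidate factor, no table and no measure of association. Section 8.4 adds "All data will be listed and summary tables will be provided" and rules out formal tests. Two further sections collect relevant data. Section 7.2.1 says "If known, any gene mutation should be noted". Section 7.6.2, on the recommended and separately consented genetic sample in PUPs and MTPs, says "The purpose of this genetic analysis is to identify markers for risk of inhibitor development".

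**Part B SAP (version 2.0).** Section 6.4.3 says that two analytes, anti-HSP-70 and inhibitors, "will be summarized in a listing that will include all values for those subjects with any positive result". The next paragraph repeats the protocol's plan for subject listings of inhibitor development without that limit, and adds Kaplan-Meier plots for which no strata are named. Section 4.1 displays efficacy and the main parts of demography by inhibitor status (none, low titer, none or low, high titer), for all subjects and for PUPs alone. It displays safety data by PUP, MTP and total only. Section 6.1.1 describes demographic and baseline data by inhibitor status where that is meaningful. Section 6.1.3 is narrower: "The following baseline characteristics of the disease history will be evaluated descriptively for the ITT, by pre-treatment (PUPs/MTPs) and overall". Its list includes family history of hemophilia and family history of inhibitor but not mutation.

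**SAP supplement (28 January 2020).** Section 2.1 adds a listing of exposure days against inhibitor value.

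**Part A SAP.** The listing limited to positives covers other antibodies: "Two laboratory analytes, Anti HSP70 and Anti BHK, will be summarized in a listing".

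**The concern.** An association is a contrast between children with the factor and children without it. It needs the number at risk on both sides, and a listing supplies neither in usable form. If the listing holds only positive children, the contrast cannot be recovered from it at all: a factor present in most of the enrolled children will be present in most of the positives, and will look like a risk factor whether or not it is one.

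The displays that do have an inhibitor-free column are efficacy and demography. Family history of inhibitor sits in the one baseline table that the SAP presents by PUP/MTP and overall only. Mutation class has no named place.

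Two things are at stake. First, the purpose stated in Protocol 8.3 would be pursued by reading individual records after the data are known, with no factors fixed in advance. Second, Part B is uncontrolled, so its inhibitor rate is read against outside experience. That reading depends on the risk mix of the enrolled children, which is only partly shown. The rate matters: under Protocol section 4 it can suspend enrollment, and the SAP introduction calls inhibitors the most significant current treatment complication.

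**Working it through.** The documents give no figure for risk-factor analysis, so there is no figure to reproduce. The check has two parts.

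**1. What positives-only data can identify.**

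Inputs:
- Part B size: 50 (Protocol 8.6: at least 25, plus about 25 more).
- Children with an inhibitor: 25. This is an assumption at the upper end, from the SAP introduction's figure of up to half.
- Positives carrying some factor F: 18 of 25. This is an assumption for illustration.

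Let C be the number of the 50 who carry F. Then RR = (18/C) / (7/(50 − C)).

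| Carriers C | Risk in carriers | Risk in non-carriers | RR |
|---|---|---|---|
| 36 | 18/36 = 50% | 7/14 = 50% | 1.00 |
| 30 | 18/30 = 60% | 7/20 = 35% | 1.71 |
| 25 | 18/25 = 72% | 7/25 = 28% | 2.57 |
| 20 | 18/20 = 90% | 7/30 = 23% | 3.86 |

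A listing of the 25 positives looks the same in all four rows. A cross-table tells them apart. In the third row it gives 72% (exact 95% CI 51 to 88%) against 28% (12 to 49%).

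The result does not depend on the 50% incidence or on the 18. Take 15 carriers among 25 positives: RR is 2.25, 1.50, 1.00 or 0.64 when 5, 10, 15 or 20 of the 25 negatives carry F. Take 15 inhibitors with 9 carriers: RR runs from 3.19 (7 of 35 negatives carry F) through 1.76 (14) and 1.00 (21) to 0.53 (28).

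**2. What a table using both groups could deliver.** With 50 children split 25/25 on the factor and two-sided alpha 0.05 (an assumption; the documents plan no test), power is:
- 34% for inhibitor risks of 20% against 40%
- 30% for 30% against 50%
- 45% for 25% against 50%
- 85% for 20% against 60%

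At 80% power, 30% against 50% would need 93 per group. Only large differences would show, so the table should carry estimates and intervals and be labelled exploratory.

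**Where each factor stands in the visible Part B SAP text.**
- Race and age at Screening: by inhibitor status, where meaningful (6.1.1).
- PUP/MTP: inhibitor frequency is shown by this split (6.4.3 with 6.4.4).
- Family history of inhibitor: PUP/MTP and overall only (6.1.3).
- FVIII mutation: not named.
- Age at first exposure and reason for first study infusion: no display by inhibitor status is named.

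**The case against.** A reader might infer that the plan looks for risk factors only in a listing of inhibitor-positive children, so that there is no comparison group and no factor could ever be shown to be associated. The documents do not support that, for four reasons.

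- Protocol 8.3 does not restrict its listing to positives. The restriction comes from one sentence in SAP 6.4.3 about laboratory analytes. The same section and the supplement have inhibitor listings with no stated limit, and Protocol 8.4 and SAP 4.1 say all data are listed.
- Inhibitor-free subjects are a column for efficacy and main demography (SAP 4.1, 6.1.1, 6.2.2), so some descriptive contrasts are planned.
- The SAP puts full table detail in separate specifications that are not available here. It covers an interim analysis, and the genetic work is a separately consented exploratory sub-study. Mutation may therefore be tabulated elsewhere. One can say only that the SAP text does not name it.
- Risk-factor identification is neither a primary nor a secondary objective, the wording in 8.3 is tentative, and no tests are planned.

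All of this stands, and it limits the point. It does not remove it. Unrestricted listings leave the reader to build the cross-table by hand. The supplement's listing pairs exposure days with inhibitor values and names no clinical factor. The wording in 6.1.1 fixes nothing in advance, and 6.1.3 leaves out the inhibitor split for the table that holds family history of inhibitor. A descriptive contrast needs no test, but it does need a denominator.

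**Conclusion.** The point holds in a limited form. For a purpose the protocol itself states, a listing is the wrong main tool, and the visible Part B SAP text does not provide the simple cross-table that would serve it for disease history and mutation. The arithmetic shows the size of the ambiguity in positives-only data: the same 18 of 25 fits a risk ratio from 1.00 to 3.86. That range is illustrative and rests on an assumed 50 children, 25 inhibitors and four assumed carrier counts. It applies only to a listing of positives, not to every listing planned.

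It would go too far to say that the plan has no inhibitor-free comparison or that no association could be described. It would also go too far to say that mutation is missing from every table, because the table specifications cannot be checked. The primary analysis and the inhibitor rate are not affected. This is an inexpensive improvement to a descriptive safety display.

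**What to change.** 1. **SAP Part B 6.1.3.** Add the inhibitor-status columns defined in 4.1 to the disease-history table.
2. **SAP Part B 6.4.3.** Add one exploratory table of children with an inhibitor (all; high titer) over number at risk, with exact 95% CI, by factors already collected and fixed before onset:
   - family history of inhibitor
   - FVIII mutation class where recorded, with an unknown row
   - race
   - PUP/MTP
   - age at first exposure
   - reason for first study infusion, with a note that for MTPs this is not the first FVIII exposure
3. **Denominator.** State it explicitly. Show all treated Part B children, and also the Protocol 8.3 rule under which an inhibitor-free child counts only after at least 50 ED.
4. **Protocol 8.3.** Refer to this table for the stated purpose and call it exploratory.

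The cost is one new table and extra columns in another, with no new data collection. The downside is precision: with about 50 children the cells are small and the intervals wide. The mutation row will be only as complete as the records, since mutation is noted only if known and the genetic sample needs separate consent. The table should be read as description, not as evidence that a factor does or does not matter.
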